#### Measures

#### Table 2: Study Measures

			6	12
Legend: EHR: Electronic Health Record; S: Survey; M: Mobile		10	m	m
app; F: Facilitator Records	BL	wk	0	0
Flow data (recruitment, enrollment, intervention adherence and				
fidelity, data collection rates)	х	Х	Х	х
Demographic and health-related characteristics				
Demographics, physical & mental health characteristics, military				
sexual trauma screen, medication use, prior treatment for pain,				
pain over past 6 months (S, EHR)	х			
EFFECTIVENESS MEASURES				
Primary Outcome				
Pain Intensity and Interference (Brief Pain Inventory Total Score;				
BPI) (S)	х	х	х	х
Secondary Outcomes				
Physical function, anxiety, depression, fatigue, sleep disturbance,				
participation in social roles and activities, patient-ratings of				
improvement, PTSD (S)	х	Х	х	Х
Process Measures				
Medication, health care utilization related to pain treatment (S,				
EHR)	х	х	х	х
Satisfaction (S)		х		
Adverse events (S; Veteran report; events reported to C-IRB)		Х	Х	Х
Pain management self-efficacy Pain Self-Efficacy Questionnaire'				
PSEQ) (S)	х	х	х	х
Pain catastrophizing, Pain Catastrophizing Scale (PCS) (S)	х	Х	Х	Х
Applied Mindfulness Process Scale (AMPS) (S)	х	Х	Х	Х
Perceived stress (NIH Toolbox Perceived Stress Fixed Form) (S)	х	х	Х	Х

LAMP Version 16, March 25, 2024 VA Central IRB Protocol Template - version 10/26/2012 Page 41 of 60

Amount of meditation practice, app use, and class attendance (M,				
F, S)		Х	х	х
Use of non-pharmacological pain management strategies (S)	Х	Х	х	Х
COVID-19 questions	х			

**Baseline Measures** will include demographic data (assessed by self-report and the EHR) and clinical data (assessed by the EHR) to capture common mental health comorbidities (e.g., depressive disorder, PTSD, anxiety, sleep-related disorders, and substance use disorders), medication use, and prior treatment for pain. These will be assessed by the baseline survey. We will also include the Pain Management Collaboratory Coronavirus Pandemic (COVID-19) Measures, comprised of seven items assessing the potential impacts of the coronavirus pandemic.

**Our Primary Outcome will be pain severity and functioning**, defined as a change in the Brief Pain Inventory (BPI) total score (assessed by survey). The Brief Pain Inventory (BPI) assesses two key domains—intensity and interference—recommended for pain studies and has been validated in primary care. The BPI is the average of pain intensity and pain interference scores. The pain intensity score is an average of 4 ratings of 0 (no pain) to 10 (pain as bad as you can imagine) for current, least, worst, and average pain in the past week. The pain interference score averages seven ratings, 0 (does not interfere) to 10 (interferes completely), of interference with general activity, mood, walking ability, normal work, relations with other people, sleep, and enjoyment of life. The BPI has been shown to be highly responsive to change in clinical trials and to have strong internal consistency (Cronbach's  $\alpha = 0.77$ ).

**Secondary Outcomes.** To facilitate data sharing and comparison between studies we have incorporated Common Data Elements (CDEs), for use in our patient surveys. Specifically, we will use measures from the PROMIS-29 Profile v2.0 Instrument (www.nihpromis.org) as recommended by the NIH Research Task Force. This includes quality of life, emotional functioning and mental health-related outcomes (anxiety, depression), and outcomes related to fatigue and sleep. Self-reported data will also be collected on PTSD symptoms using the PTSD checklist (PCL), version C, DSM-V update, and patient satisfaction (using a short measure used by investigators [name] and [name]). These outcomes will be assessed via survey.

Adverse events will be monitored throughout the study period, using a process similar to other MBIs with Veterans. Specifically, Veterans will be given contact information encouraged to report exacerbation of symptoms or adverse effects to the class facilitators or study coordinator.

We will use electronic medical data from VA health care records to assess other measures of chronic pain burden including change in analgesic use (including opioids), and frequency and health care utilization (e.g. MRIs, injections, hospitalizations, surgery). Among those prescribed opioids, we will assess change in opioid use from baseline using VA pharmacy dispensing data. Opioid daily dose at any given time will be calculated as the mean dose over the prior 90 days. Established conversion tables will be used to calculate morphine-equivalent (ME) mg. Receipt

LAMP Version 16, March 25, 2024 VA Central IRB Protocol Template – version 10/26/2012 Page 42 of 60

of pain-related services outside of intervention visits will be estimated by capturing pain-related specialty visits and pain-related mental health visits. Complementary therapies are not all well captured in VA databases, but therapies with specific codes (e.g., acupuncture) will be assessed. Other complementary services may be variably recorded under general codes; for example, yoga could be coded as a recreational therapy visit.

Process Measures/Mediators will include items to assess Capabilities, Opportunities, Motivations, and Adaptive Pain-Related Behaviors that the intervention is designed to address (delineated in our Theoretical Framework, see Figure 1). Mindfulness skills will be assessed through the Applied Mindfulness Process Scale (AMPS), a 15-item validated scale will be used to assess the extent to which participants used mindfulness practice in their daily life (e.g., to "calm my emotions when I was upset," "stop reacting to my negative impulses," "relax my body when I was tense," and "stop my unhelpful reactions to situations"). Opportunities will be assessed by the amount of training and practice participants engage in, captured by the mobile application and self-report. Motivations will be assessed by increases in pain acceptance and pain management self-efficacy and decreases in pain-related fear avoidance. Pain catastrophizing will be assessed with the Pain Catastrophizing Scale (PCS). Pain management self-efficacy will be assessed with the 8-item Pain Self-Efficacy Questionnaire (PSEQ). which has been used in numerous studies with chronic pain patients. Adaptive pain-related behaviors include reduction in opioid analgesics (assessed by EHR data) and increase in use of nonpharmacologic pain management strategies (assessed by EHR data and self-report). We also will assess perceived stress, with the NIH Toolbox Perceived Stress Fixed Form Age 18+ v2.0.

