**Risk vs. Potential Benefit.** The proposed research poses "minimal risk" to subjects. There are no experimental procedures involved in this study. The potential risks to study participants include loss of privacy and confidentiality. There are no economic and minimal social risks of participating in the study. The surveys will not ask very sensitive questions and subjects can refuse to answer any question(s). The potential risks associated with the individual interviews include psychosocial stress (any research project with direct contact with human subjects contains some risk of deleterious effects due to psychosocial stress). This is true for both usual care as well as intervention groups.

Mindfulness-based interventions are regarded as relatively safe interventions. A 2018 systematic review examining the safety of randomized controlled trials of mindfulness-based interventions found very few adverse events, with no significant differences in reported adverse events between intervention and control groups. Nonetheless, we have developed a crisis management protocol to address issues involving participant safety and systematically collect safety information, including severe adverse events (SAEs), unanticipated problems (UAPs), and adverse events (AEs). In the follow up questionnaires, participants will be asked to report side effects/adverse events related to the interventions by choosing from a list generated from the literature and the investigators' experience (see below).

Since you started your participation in the study have you experienced any of the following. Check all that apply.

- 1. Increase in disturbing memories
- 2. Feeling more upset than usual when something reminded you of the past
- 3. Increased feelings of sadness
- 4. Increased feelings of anxiousness

5. Seizures

- 6. Feeling more tired or fatigued than usual
- 7. Feeling more isolated or lonely

8. Other physical or mental symptoms; please specify: \_\_\_\_\_\_

If yes, please explain further:

Specifying conditions that would trigger an immediate suspension of the research is not applicable to this minimal risk study. If information does arise that necessitates communication, the study team will contact participants by phone and providers via encrypted email.

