#### Expected participation in Phase 2 trial

We base proposed estimates on our experience conducting previous successful trials with Veterans with chronic pain (ACTION, SPACE, EPOCH, ECLIPSE). Study participants will be recruited from the Minneapolis, Indianapolis, Greater Los Angeles and Durham VA Health Care Systems, using a process successfully used in prior studies by members of our research team, and piloted during Phase 1 of this project. The four facilities have about 80,000 patients who meet our initial eligibility criteria. We estimate from our Phase 1 pilot a randomization rate of 2.5% but an increased randomization rate when using approach #2, email recruitment. Therefore, we will need to screen approximately 100,000 patients in order to reach our recruitment goal of up to 950 randomized. We want an approximately balanced sample of men and women. We estimate women will respond at up to 3 times the rate of men (approximately 4.5% for women and almost 2% for men). If we screen a large portion of the sample of eligible women (about 20,000) and about 1/3 of the eligible men (about 80,000), then we should reach our recruitment goal of up to 950 randomized, with nearly balanced men and women. Among those randomized, we are conservatively planning that up to 20% might be missing complete follow-up data but based on past work we believe the actual level of missing data will be closer

to 10-15%. Ultimately, this would yield a randomized N= up to 950 and with retention of 600 or greater participants at 6 and 12 months.

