## 6.0 Reporting

We will follow the VA Central IRB reporting requirements for all issues that must be reported (i.e. unanticipated serious adverse events (U-SAEs), unanticipated problems (UAPs), protocol deviations/violations/noncompliance, and any changes with respect to the protocol). The study staff will remain in regular contact (by phone, email, and face-to-face) to discuss study processes, progress, and any issues encountered. Any issues will be reported directly to the PI. Data will be reviewed regularly to ensure accuracy and data privacy. In the case of problems, the project coordinator will immediately discuss with the study PI. The PI in turn will report any problems to the Central IRB accordingly (e.g., completing forms 119 or 129) within 5 business days of learning of the problem(s). If there are modifications or amendments to the study the study PI will also complete the appropriate Central IRB form (i.e., 116) and wait for approval prior to implementation. Additionally, all unanticipated deaths that are related to a research study overseen by the VA Central IRB must immediately be reported orally to the VA Central IRB wia the toll-free number [contact].

The current application is for a low-risk clinical trial. The Study Coordinator and participants are not blinded to the study condition group assignment. Therefore, we believe, [name], as the PI, can be responsible for carrying out the Data Safety Monitoring Plan (DSMP) throughout the entire study period. [name] will thus be responsible for overseeing and ensuring an IRB-compliant process for reporting Adverse Events (AEs), including Serious Adverse Events (SAEs), and Unanticipated Problems (UPs), should any occur.

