## 8.0 Communication Plan

PI [name] will meet regularly with [name], the project coordinator. At these meetings, [name] will check in with [name] to ensure that the following key communications occur:

- 1. Ensure that required local site approvals are obtained
- 2. Notify the Director of any facility where the research in being conducted, but the facility is not engaged.
- 3. Keep engaged sites informed of changes to the protocol, informed consent, and HIPAA authorization
- 4. Inform local sites of any SAEs, UAPs, or interim results that may impact conduct of the study.

5. Notify all local facility directors and LSIs when the study reaches the point that it no longer requires engagement of the local facility

The study team will also review relevant sections of the protocol periodically, so that we can make sure that the different phases of the study are conducted according to the IRB-approved protocol.

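### The plan promises systematic collection of serious adverse events, but no listed source asks about or looks up hospitalization or death, so capture depends on mention or chance and may differ by arm

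*Combined protocol and SAP*

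**What the plan says.** Section 5.1 (Risk vs. Potential Benefit) states that a crisis management protocol has been developed and that the study will "systematically collect safety information, including severe adverse events (SAEs), unanticipated problems (UAPs), and adverse events (AEs". It then describes one instrument: "participants will be asked to report side effects/adverse events related to the interventions by choosing from a list generated from the literature". The checklist printed there names disturbing memories, being upset by reminders, sadness, anxiousness, seizures, fatigue and isolation. It ends with an open item for other symptoms and a request to explain.

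Table 2 in section 5.5a gives the adverse-event sources as "Adverse events (S; Veteran report; events reported to C-IRB", at 10 weeks, 6 months and 12 months. The same table's key ("Legend: EHR: Electronic Health Record; S: Survey; M: Mobile") defines the EHR as a source, and other rows use it. The adverse-event row does not.

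The text after Table 2 describes Veteran report as participants contacting class facilitators or the study coordinator. Section 6.0 covers what goes to the Central IRB, including "unanticipated serious adverse events (U-SAEs"), unanticipated problems, and unanticipated deaths related to the research.

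Elsewhere in section 5.5a, VA records are to supply "health care utilization (e.g. MRIs, injections, hospitalizations, surgery") as a measure of chronic pain burden, with no restriction by arm.

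**The concern.** Adverse effects are listed among the secondary outcomes in sections 3.0 and 5.1, so they will be reported by arm as a trial result. If hospitalizations and deaths are not actively sought, a low SAE count may reflect the method of collection rather than the safety of the interventions.

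Two features make this more than a matter of completeness. First, section 5.4a excludes active psychosis, suicidality, severe depression and poorly controlled bipolar disorder because some experts regard them as contraindications to mindfulness programs. The plan thus recognizes psychiatric risk, yet no listed source would look up a psychiatric admission. Second, staff contact differs sharply by arm. Events that surface through contact are therefore more likely to be heard of in the intervention arms, which could create or hide a between-arm difference.

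**Working it through.** This is a question of ascertainment. The plan states no figure to reproduce, so the check is to take each source and ask whether it could find an admission or a death.

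1. **Survey checklist (section 5.1).** It has seven named symptoms, an open item and a request to explain, and it is asked at three time points. It prompts for seizures. It does not ask about hospitalization, emergency care or any other seriousness criterion, so a ticked symptom cannot be graded as serious unless the respondent adds the detail unasked. It cannot capture a death.

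2. **Veteran report (section 5.5a).** This is spontaneous by design, and the named recipients are facilitators and the coordinator.

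3. **Events reported to the Central IRB (section 6.0).** The reporting clock starts when the team learns of a problem. This route forwards known events and contains no step that finds them.

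4. **EHR (section 5.5a).** Hospitalizations are to be drawn from VA records, but nothing routes them to safety review. Table 2 confines the utilization row to care connected with pain treatment, and the EHR paragraph does not mention deaths. All-cause admissions and deaths are therefore not clearly within the extract as described.

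**Scheduled staff contact by arm (section 5.1):**

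| Arm | Scheduled contact during the program |
|---|---|
| Mobile+Group | 8 facilitated sessions of about 1.5 hours (8 × 1.5 = 12 hours) |
| Mobile | 3 check-in calls |
| Usual care | none described; assignment call and letter, then the common follow-up surveys |

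The self-harm and distress procedure in section 5.1 is triggered by contact in group or by phone, so it follows the same gradient.

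**Size of the group in whom survey capture is weakest.** Section 5.6 plans conservatively that "up to 20% might be missing complete follow-up data", and expects 10–15%.

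- At 250 per arm: 250 × 0.20 = 50 per arm, and 3 × 50 = 150 of 750.
- At the ceiling of 950: 950 × 0.20 = 190.
- At the 10% end: 750 × 0.10 = 75 and 950 × 0.10 = 95.

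These count people without *complete* follow-up. Someone who misses one survey is included, so the figures are upper bounds on those with no safety survey at all.

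**The case against.** The strongest reply is that the visible text is not the whole safety system. The crisis management protocol and the mental health protection protocol named in section 5.1 are not reproduced, and either might hold an SAE procedure. The survey is also not passive: it prompts every respondent three times, covers the whole period since the start of participation, and leaves room to describe an admission. Table 2 also collects pain-related utilization partly by survey. Finally, this is a minimal-risk behavioral trial, and all-cause surveillance will mostly return unrelated events.

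Much of this stands, and it limits the point to hospitalization, death and seriousness in the text available. It does not remove the gap: no visible step seeks these events, and none treats the three arms alike.

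A reader might go further in four ways that the documents do not support:

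- *Non-responders leave no record.* Sections 5.5a and 7.0 describe repeated reminders by several methods. Section 5.5a plans record access to trace people who are hard to reach, and section 5.3a requires an emergency contact. Events can come to light this way, though not systematically.
- *Local sites must be told of every SAE.* Section 8.0 reads "Inform local sites of any SAEs, UAPs, or interim results that may impact conduct of the study"; the closing qualifier can govern the whole list.
- *Sites would apply two different filters*, because section 5.1 expands SAE as *severe* and other sections as *serious*. All study steps are run from Minneapolis and reporting sits with the PI, so this is a wording slip.
- *Hospitalization data for safety are already in hand.* The stated scope is pain-related, and deaths are not mentioned.

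**Conclusion.** The concern holds in this limited form. The commitment to collect SAEs systematically is not met by the sources listed in Table 2. On the visible text, hospitalizations and deaths enter the safety record only when a participant mentions them or staff happen to learn of them. Capture may be uneven between the intervention arms and usual care, and it is weakest among the 75–150 of 750 (95–190 of 950) who may lack complete follow-up on a 10–20% assumption.

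The number of events that would be missed cannot be stated, because the documents give no admission or death rate. The conclusion assumes that the two protocols not reproduced contain no active SAE search; if one does, the remedy is to cite it in Table 2. That EHR capture would cover every arm is inferred from the absence of any arm restriction in section 5.5a. The primary efficacy analysis is unaffected.

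**What to change.** 1. In the adverse-event row of Table 2, add EHR as a source for all three arms. Define it as all-cause VA hospitalizations and deaths from randomization to 12 months, queried at the existing 10-week, 6-month and 12-month points. The PI classifies each event under section 6.0, and results are reported by arm for all randomized participants, including survey non-responders.
2. Add one item to the follow-up survey asking whether any reported symptom led to hospital or emergency care. This also reaches care outside the VA.
3. In section 5.1, change *severe* to *serious* in the expansion of SAE.

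The infrastructure is largely described already. Section 5.5a gives access to frequently updated mirrors of the VHA record, and section 5.3a seeks a HIPAA waiver for the whole study. The costs are an extract somewhat wider than the pain-related one now described (it must add all-cause admissions and deaths), repeated queries during follow-up, PI time to classify events, and a longer list in which many events will be unrelated to the interventions. Events outside the VA will still depend on self-report. No participants, visits or changes to the efficacy analysis are needed.

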### 5.5b. Study Evaluations for VA Employee Stakeholders (Aim 2b)

Note: These questions may be tailored to different subgroups.

- 1. Who are the decision-makers we would need to get buy-in from at your facility or VISN, in order to implement this program? (Probe for roles; who are they, may include interviewee...)
- 2. What would these decision-makers need to persuade them that this program is worth implementing, even on a trial basis?
- 3. Who else is critical to implementing this program and making is successful?
- 4. What are the obstacles we would need to address in order to implement this program and make it a success?
- 5. What are some things that would help us successfully implement this program?

Demographic questions (asked via Qualtrics FedRAMP online survey):

- 1) What is your age?
- 2) How would you describe your gender? (Select one.)
  - a. Man (1)
  - b. Woman (2)
  - c. Another gender category, please specify: (3)
  - d. Decline to answer (4)
- 3) What is your ethnicity? (Choose the one with which you MOST CLOSELY identify.)
  - a. Hispanic or Latino (1)

LAMP Version 16, March 25, 2024 VA Central IRB Protocol Template – version 10/26/2012 Page 43 of 60

- b. Not Hispanic or Latino (2)
- 4) What is your race? (Choose all those with which you identify.)
  - a. Black or African American (1)
  - b. American Indian/Alaska Native (2)
  - c. Asian (3)
  - d. Native Hawaiian/Pacific Islander (4)
  - e. White (5)
- 5) What is your occupational role?\_\_\_\_\_

#### 5.6 Analysis Plan

#### AIM 1: EFFECTIVENESS

Primary effectiveness will be assessed by **pain severity and functioning** over the 12-month follow-up (Brief Pain Inventory total score). Secondary analyses will examine the effectiveness of the intervention separately by gender.

Secondary outcomes will include measures captured in health care records (e.g., medication prescription/refills, health care visits for pain management) as well as patient-reported measures related to pain, comorbid mental health conditions and function, expected mediators of treatment effects, patient satisfaction, and adverse events. We will also explore patient characteristics that may predict treatment response. These outcomes will be assessed at baseline, 10 weeks, 6 months, and 12 months. Aim 2.1 methods involving recruitment, study design, intervention, data collection, and outcomes are described in the prior section. Methods related to expected participation, data analysis, and data coordination and management are described in the following section.

